12.2 Primary efficacy Objective

 Effect of AP1189 vs. placebo in subjects with severe active RA (CDAI > 22), undergoing up-titration with MTX, by showing a change in CDAI from severe (CDAI > 22) to moderate (CDAI ≤ 22) after 4 weeks treatment compared to baseline.

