23.5 Efficacy Analysis

All efficacy endpoints will be evaluated by treatment group using descriptive statistics. Confidence intervals will be presented where appropriate.

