### 2.1.3 Primary Efficacy Objective

• Effect of AP1189 vs. placebo in subjects with severe active RA (CDAI > 22), undergoing uptitration with MTX, by showing a change in CDAI from severe (CDAI > 22) to moderate or lower (CDAI ≤ 22) after 4 weeks treatment compared to baseline.

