## **3 STATISTICAL ANALYSIS CONSIDERATIONS**

## 3.1 Types of Analysis

All safety parameters (ECG, vital signs, AEs/SAEs, laboratory abnormalities, etc.) will be summarized by treatment and time point. Continuous variables will be summarized using n, mean, standard deviation, median, minimum, and maximum values. For categorical (nominal) variables, the number

of patients per category, and percent of the total number of patients will be presented.

Descriptive statistics (continuous and categorical variables summarized as above) will be used for an exploratory description of exposure. Plasma concentrations will be used to measure exposure.

All efficacy endpoints will be evaluated by treatment group using descriptive statistics (continuous and categorical variables summarized as above). Confidence intervals will be presented where appropriate.

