  - Health Assessment Questionnaire (HAQ-DI)
  - C-Reactive Protein (CRP)

The Patient Global Assessment of Disease Activity RA, the Investigator Global Assessment of Disease Activity RA, and the CDAI score will be presented in absolute values and values relative to placebo by dividing the mean, median, min, and max values for each active treatment group by the corresponding value for the placebo group.

An indicator noting whether a subject received rescue treatment (joint injections with corticosteroid) during the 4-week treatment period (Baseline visit to Visit 6) will be constructed. The team will go

Study SynAct-CS002 – Statistical Analysis Plan

through the concomitant medication listings to define which subjects received rescue treatment before analyses.

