## 3.7 Interim Analysis

An interim analysis has been performed, evaluating the first (minimum) 24 subjects from Part 1 of the trial in order to assess the safety and efficacy of the investigational product before proceeding to Part 2. Version 1 of this analysis plan was used for the interim analysis.

All safety parameters (ECG, vital signs, AEs/SAEs, laboratory abnormalities, etc.) and efficacy data for the primary efficacy endpoint were summarized by treatment and time point for the subjects included in Part 1 of the study, i.e., the following tables (see Appendix 4 for details) were presented (any MedDRA coding of AEs will not be performed for the interim):

• Table 11.4.1.3 (CDAI score)

Study SynAct-CS002 – Statistical Analysis Plan

- Table 11.4.1.4 (CDAI score, change from baseline to week 4)
- $\circ~$  Table 11.4.1.5 (CDAI score, change from severe (CDAI > 22) to moderate (CDAI  $\leq$  22) at week 4 compared to baseline)
- Table 12.2.1.1 to Table 12.5.5.1 (all safety tables).

Listings showing the following data were also presented:

- Patient disposition (including end of study information), i.e., the following listings (see Appendix 4 for details):
  - Listing 6.4.1 (Visit Registration)
  - Listing 6.4.2 (Informed Consent, Randomization, Subject Summary)
  - Listing 6.4.3 (Alcohol Consumption)
  - Listing 16.2.8.1 TB and Serology Tests)
  - Listing 6.4.10 (Inclusion Exclusion Criteria)
- Demographics and baseline characteristics, i.e. the following listings (see Appendix 4 for details):
  - Listing 16.2.4.1 (Demographics)
  - Listing 6.4.5 (Vital Signs)
  - Listing 16.2.4.3 (Age)
- Safety profiles (laboratory values, adverse events, related adverse events, serious adverse events (SAE), adverse events leading to withdrawal), i.e., the following listings (see Appendix 4 for details):
  - Listing 16.2.8.2 (Blood Biochemistry)
  - Listing 16.2.8.3 (Blood Haematology)
  - Listing 16.2.7.1 (Adverse Event Q).
- Efficacy data for the primary study endpoint
  - Listing 16.2.6.3 (CDAI)
  - Listing 16.2.6.7 (Changes from baseline in CDAI)

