#### 6.1.1 Description of primary efficacy variables

| Variable (CRF annotation)   | How to be presented                                    |
|---|--|
| Patient Global Assessment of Disease Activity RA,
cm (PGADA, dataset CDAI)                                   | n, mean (95% CI), sd, median, min, max, by
visit    |
| Patient Global Assessment of Disease Activity RA,
cm, relative to placebo (derived, see Section 3.6)         | Mean, median, min, max, by visit, country, and site    |
| Investigator Global Assessment of Disease
Activity RA, cm (IGADA, dataset CDAI)                              | n, mean (95% CI), sd, median, min, max, by
visit    |
| Investigator Global Assessment of Disease
Activity RA, cm, relative to placebo (derived, see
Section 3.6) | mean, median, min, max, by visit, country,
and site |
| CDAI score calculated (CDAI)  | n, mean (95% CI), sd, median, min, max, by visit       |

Study SynAct-CS002 – Statistical Analysis Plan

| CDAI score calculated, relative to placebo (derived, see Section 3.6)  | Mean, median, min, max, by visit, country, and site          |
|--|--|
| CDAI change from baseline to week 4 (derived, see Section 3.6)   | n, mean (95% CI), sd, median, min, max, by
visit          |
| Proportion of subjects with a change in CDAI
score from severe (CDAI > 22) to moderate or
lower (CDAI ≤ 22) at week 4 compared to
baseline (derived, see Section 3.6) | <pre># patients and % /category (2 categories: Yes/No)</pre> |

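### The primary efficacy objective compares AP1189 with placebo, but the SAP text defines no dose-minus-placebo estimate with a confidence interval for either primary variable

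*SAP*

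**What the plan says.** Both documents state a comparative primary efficacy objective. Protocol 12.2 has "Effect of AP1189 vs. placebo in subjects with severe active RA (CDAI > 22), undergoing up-titration with MTX", and SAP 2.1.3 repeats it. The two primary variables are the mean change in CDAI from baseline to week 4 and the proportion moving from CDAI > 22 to CDAI ≤ 22.

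The planned analysis is within arm. Protocol 23.5 says "All efficacy endpoints will be evaluated by treatment group using descriptive statistics" and adds "Confidence intervals will be presented where appropriate"; SAP 3.1 says the same. Protocol 23.5.1 asks, in each group, for an interval for the mean change and a Clopper-Pearson interval for the proportion. SAP 6.1.1 lists CDAI change as n, mean with 95% CI, SD, median, minimum and maximum. It lists the responder proportion as a count and percentage, with no interval.

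Two places speak of results relative to placebo:

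- SAP 3.6 (Efficacy analysis) defines them for the Patient Global, Investigator Global and CDAI scores by "dividing the mean, median, min, and max values for each active treatment group by the corresponding value for the placebo group". In 6.1.1 these appear as "Mean, median, min, max, by visit, country, and site", with no interval.
- SAP 3.8 says that, for the primary endpoints by country and site, results will also be expressed relative to the placebo group's effect. It gives no formula, scale or interval.

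The CDAI tables that SAP 3.7 names, such as "Table 11.4.1.4 (CDAI score, change from baseline to week 4"), and the tables added in the revision history (11.4.1.60 to 11.4.1.80) have titles that mention no difference from placebo.

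**The concern.** The objective asks how AP1189 compares with placebo, and the SAP text does not say what number will answer that. Because 3.8 commits the sponsor to placebo-relative results for the primary endpoints, someone must choose the scale (difference or ratio), whether to adjust for baseline, and the interval method. SAP 1.1 says the plan exists to prevent choices of that kind being made post hoc.

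The one contrast that is defined is a poor substitute. It compares raw scores, not change or response. It does not adjust for baseline and has no stated uncertainty. Ratios of minima and of maxima do not estimate a treatment effect, and a ratio is undefined if the placebo minimum is 0.

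**Working it through.** **Inputs.** Protocol 23.2.1: SD of change 3, at least 30 per group that proceeds to Part 2. Protocol 23.2.2: SD 2.5, 15 per group. Protocol 15.3 and 15.4: Part 1 has 8 on 50 mg, 8 on 100 mg and 4 + 4 on placebo. Part 2 has 22/22/22 (Design 3) or 44 vs 22 (Designs 1 and 2). Combining parts gives placebo 4 + 4 + 22 = 30, a dose in Design 3 8 + 22 = 30, and the selected dose in Design 1 or 2 8 + 44 = 52. Pooling of the Part 1 placebo groups is implied by the target of 30 per group.

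**Formula.** Width of the 95% CI not exceeded with 80% probability: 2 × t(0.975, v) × SD × √(χ²(0.80, v)/v) × √f. Here f = 1/n and v = n − 1 for one arm; f = 1/n₁ + 1/n₂ and v = n₁ + n₂ − 2 for a difference.

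**The plan's own figures reproduce.**

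- n = 25, SD 3: 2 × 2.064 × 3 × 1.110 × 0.200 = 2.75 (protocol: about 2.8)
- n = 30, SD 3: 2 × 2.045 × 3 × 1.101 × 0.183 = 2.47 (about 2.5)
- n = 15, SD 2.5: 2 × 2.145 × 2.5 × 1.139 × 0.258 = 3.15 (about 3.2)

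These are correct one-arm widths and are labelled as such.

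**Width for dose minus placebo, unadjusted.**

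- 30 vs 30, SD 3: 2 × 2.002 × 3 × 1.073 × 0.258 = 3.33
- 52 vs 30, SD 3: 2 × 1.990 × 3 × 1.063 × 0.229 = 2.91
- 15 vs 15, SD 2.5: 2 × 2.048 × 2.5 × 1.102 × 0.365 = 4.12

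The 30 vs 30 width is 3.33/2.47 = 1.35 times the one-arm width. All scale with the SD: 30 vs 30 at SD 6 gives 6.66.

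**Responder risk difference.** With assumed rates of 30–70% in each arm, the Newcombe 95% interval is 44–48 percentage points wide at 30 vs 30 and 40–43 at 52 vs 30.

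**What the raw-score ratio can miss (illustrative means).** Suppose week-4 CDAI is 28 in both arms, so the ratio is 28/28 = 1.00. With baselines of 40 (active) and 36 (placebo), the difference in change is (28 − 40) − (28 − 36) = −4. With the baselines reversed it is +4.

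**Baseline imbalance under no effect.** Assumed, not in the documents: baseline mean 34–39, SD 7.5–8.9, mean change −8 to −16. The SE of the baseline difference at 30 vs 30 is 7.5 × 0.258 = 1.94 to 8.9 × 0.258 = 2.30, so a 2-point imbalance is about 1 SE. The week-4 ratio is then (39 − 8 + 2)/(39 − 8) = 1.06 to (34 − 16 + 2)/(34 − 16) = 1.11.

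**Gain from adjustment.** Let b be the baseline SD, s the change SD and r their correlation. The week-4 raw-score variance is b² + s² + 2rbs = s²(1 − r²) + (b + rs)². It cannot fall below the baseline-adjusted variance s²(1 − r²), ignoring one degree of freedom and small-sample imbalance. For r from 0 to −0.5 and b of 7.5–8.9, the raw difference has 2.5–3.1 times the adjusted SE at s = 3, and 1.01–1.41 times at an assumed s of 9–12. These factors describe a difference of raw means, not the ratio in 3.6.

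**The case against.** **The plan is openly descriptive.** It states no test, power or between-arm effect, and sizes the trial on a one-arm interval. A reader might infer that a hypothesis test is missing or that the design cannot support a comparison. The documents support neither inference. An estimate with an interval is still descriptive and fits the provision for intervals where appropriate. An unadjusted difference can be worked out from the planned per-arm n, mean, SD and counts. The baseline-adjusted difference cannot.

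**The raw ratio is not the only placebo-relative output.** A reader might infer that it is. SAP 3.8 plans a second, on the primary endpoints themselves. What 3.8 lacks is a definition.

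**The baseline imbalance is visible.** The ratio is shown by visit and CDAI is scored at baseline, so a baseline ratio would stand beside the week-4 ratio. That stands: the imbalance is displayed, but it is not adjusted for.

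**The shells may hold a difference.** Appendix 4 is a separate document, most titles from 11.4.1.1 to 11.4.1.59 do not appear in the text, and a title does not show a table's columns. SAP 8.4 also mentions p-values among calculated efficacy data, although no test is defined. A reader might infer that the full plan has no difference from placebo; the available text cannot show that.

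**The raw contrast is not always less precise.** At an assumed change SD of 9–12 its SE is 0.9–1.4 times that of the unadjusted difference in change, so it can be the more precise of the two. This does not hold against the baseline-adjusted difference.

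**Conclusion.** The point holds as a gap in the analysis text. The objective is comparative, both primary variables have only per-arm summaries, SAP 3.8 leaves its placebo-relative results undefined, and the only contrast with a formula is a ratio of raw scores without an interval.

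The design and the protocol's one-arm precision figures are not in question. The widths for the difference (3.3, 2.9 and 4.1 points) rest on the protocol's SDs of 3 and 2.5 and on combining Parts 1 and 2. The imbalance, SE and responder figures rest on the stated assumptions and show scale only.

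Confidence is medium because the Appendix 4 shells were not available. The gap should be fixed: it concerns the primary objective and can be closed from data already collected.

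**What to change.** Change the SAP only:

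- In 3.1 and 6.1.1, prespecify for each retained dose minus placebo (a) the difference in mean CDAI change at week 4 with 95% CI, adjusted for baseline CDAI, and (b) the responder risk difference with 95% CI by a named method such as Newcombe.
- In 3.8, define the placebo-relative results as these differences. Drop the ratios of median, minimum and maximum from 3.6 and 6.1.1.
- State that the contrasts apply to the main study, the sub-study and the pooled data (SAP 3.5), with the per-protocol repeat (SAP 3.2).
- Record the addition in 3.12 as an analysis beyond the protocol's per-arm descriptive statistics.
- Add the per-arm Clopper-Pearson interval to the responder row of 6.1.1, to match protocol 23.5.1.
- If the precision of the difference is reported, say that it depends on the assumed SDs.

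The cost is SAP text and one or two tables. No new data, patients or protocol amendment are needed. A factor for randomisation cohort (A/B, C/D, Part 2) is optional. Compared at equal degrees of freedom (84) and SD 3, it raises f from 0.0667 to 0.0703 in Design 3 (width 3.27 to 3.36) and from 0.0526 to 0.0577 in Design 1 or 2 (2.90 to 3.04).

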## Pharmacokinetic analysis

Plasma concentration values below the level of quantification will be set to LoQ/2 for the analysis.

#### Safety analysis

The QT interval on the ECGs is corrected from Bazett, Hodges or ECAPS to Fridericia. The laboratory values from the different sites may be reported in different units, which will be corrected to:

| Variable                     | Unit to be used
in
analyses/report | Conversion formula(s)                       | Comments   |
|------------------------------|--|---|--|
| Corrected QT Interval (QTc)  | QTc Fridericia                           | QTcF = QT/(RR 1/3 )  | The reported QT and RR
intervals will be used to
calculate QTcF. |
| HbA1c                        | mmol/mol                                 |   | mmol/L used at sites in
Moldova and Bulgaria                        |
| White blood cell             | 10E9/L                                   |   | g/dl used at some sites  |
| Neutrophils                  | 10E9/L                                   |   | g/dl used at some sites  |
| Lymphocytes                  | 10E9/L                                   |   | g/dl used at some sites  |
| Monocytes                    | 10E9/L                                   |   | g/dl used at some sites  |
| Eosinophils                  | 10E9/L                                   |   | g/dl used at some sites  |
| Basophils                    | 10E9/L                                   |   | g/dl used at some sites  |
| Hemoglobin                   | mmol /L                                  |   | g/dl used at some sites  |
| Red blood cells (RBC)        | 10E12/L                                  |   | g/dl used at some sites  |
| Thrombocytes                 | 10E9/L                                   |   | g/dl used at some sites  |
| Alanine transaminase (ALT)   | U/L                                      | $(\mu kat/L) *60 = U/L^2$                   | µkat/L used at some sites  |
| Aspartate transaminase (AST) | U/L                                      | $(\mu kat/L) *60 = U/L^2$                   | µkat/L used at some sites  |
| γ-glutamyltransferase (GGT)  | U/L                                      | $(\mu kat/L) *60 = U/L^2$                   | µkat/L used at some sites  |
| Bilirubin (total)            | μmol/L                                   |   |  |
| Bilirubin (conjugated)       | μmol/L                                   |   | µkat/L used at some sites  |
| Alkaline phosphatase (ALP)   | U/L                                      | $(\mu kat/L) *60 = U/L^2$                   | µkat/L used at some sites  |
| Glucose (non-fasting)        | mmol/L                                   |   |  |
| TSH                          | 10E3/L                                   | (U/L) /1000 = mIU/L
mIE/L                |  |
| Total T3                     | nmol/L                                   |   |  |

Study SynAct-CS002 – Statistical Analysis Plan

| Free T3                  | pmol/L | Sweden and Denmark
measure Total T3, while
Norway measures Free T3. |
|--------------------------|--------|---|
| Free T4                  | pmol/L | Some sites measure Total T4   |
| Potassium                | mmol/L |   |
| Sodium                   | mmol/L |   |
| Chloride                 | mmol/L | Site 04 measures chloride in whole blood, the other sites in plasma       |
| Calcium                  | mmol/L |   |
| Albumin                  | g/L    |   |
| Creatinine               | μmol/L |   |
| C-Reactive Protein (CRP) | mg/L   |   |
| Urea                     | mmol/L |   |

 https://www.clinigate.com/clinicalc/corrected-qt-interval-qtc.php

 http://unitslab.com/node/55

Conversion formulas available from relevant medical sources will be used and documented in the Statistical Report.

All the clinical sites are using their local laboratory to measure safety parameters, which means that different reference intervals will apply.

Additional units might be collected and will be converted according to standard practice.

Lab values reported as a non-numerical value (e.g., '<1') will be converted to an appropriate numerical value for numerical analyses (e.g., calculation of mean values). The team will decide the numerical value to be used before analyses. Lab values below the level of quantification will be set to LoQ/2 for the analyses.

Urine culture results will be entered as free text. The text entries will be combined into categories for summaries, where the categories will be decided by the team before analyses.

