13 SAFETY ENDPOINTS

13.1 Primary Safety Endpoint

The safety of AP1189 against placebo by evaluating adverse events (AEs), serious adverse events (SAEs), and laboratory abnormalities.

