19.1.1.1 MTX Treatment Instruction in Case of Elevation in Liver Enzymes

It is recommended with more frequent blood test in case of elevation of liver enzymes.

Transaminase Increase:

Laboratory Value	Action
ALT and/or AST increases	IMP and MTX remains unchanged.
up to > 1 to ≤ 3 x Upper Limit of Normal (ULN)	It is recommended with more frequent blood test in case of elevation of liver enzymes.
And bilirubin is within the normal range	

Protocol Code Number: SynAct-CS002

Laboratory Value	Action
ALT and/or AST increases > 3 to ≤ 5 x ULN	Pause IMP dosing until ALT and/or AST < 3 x ULN and follow recommendations above for > 1 to < 3 x ULN
And bilirubin is within the normal range	Upon normalization of ALT and/or AST, IMP resumes For persistent increases > 3 x ULN, discontinue IMP
ALT and/or AST > 5 x ULN	MTX and IMP discontinue
Bilirubin > normal range	MTX and IMP treatment discontinue

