### 2.1.2 Primary Safety Variables

AEs, SAEs, and laboratory abnormalities.

See section 3.6 for details of the calculation of primary safety variables.

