#### 7.9.2 Biochemistry

| Variable (CRF annotation) | How to be presented |
|---------------------------|---------------------|
|---------------------------|---------------------|

Study SynAct-CS002 – Statistical Analysis Plan

|   | 1   |
|---|---|
| Blood sample collected for analysis of
Biochemistry (BLBPERF)  | # patients and % /category, by visit
(2 categories: Yes/No)  |
| Biochemistry sample Date (BLBDT)  | Listing only  |
| Biochemistry sample Time (BLBTM)  | Listing only  |
| Alanine transaminase (ALT), collected unit  (ALT, ALT_U)                                    | Listing only (units converted to U/L)   |
| Alanine transaminase (ALT), U/L (derived from ALT above)  | n, mean, sd, median, min, max, by visit   |
| Alanine transaminase (ALT), Out of range and
Clinically significantly abnormal (ALT_OR, ALT_CS)      | <pre># patients and % /category (1 category ALT_OR; Yes, 2 categories ALT_CS; Yes/No), by visit</pre> |
| Aspartate transaminase (AST), collected unit
(AST, AST_U)  | Listing only (units converted to U/L)   |
| Aspartate transaminase (AST), U/L (derived from AST above)  | n, mean, sd, median, min, max, by visit   |
| Aspartate transaminase (AST), Out of range and
Clinically significantly abnormal (AST_OR,
AST_CS) | <pre># patients and % /category (1 category AST_OR; Yes, 2 categories AST_CS; Yes/No), by visit</pre> |
| γ–glutamyltransferase (GGT), collected unit (GGT,
GGT_U)   | Listing only (units converted to U/L)   |
| γ–glutamyltransferase (GGT), U/L (derived from
GGT above)  | n, mean, sd, median, min, max, by visit   |
| γ–glutamyltransferase (GGT), Out of range and
Clinically significantly abnormal (GGT_OR,
GGT_CS)  | # patients and % /category
(1 category GGT_OR; Yes, 2 categories
GGT_CS; Yes/No), by visit      |
| Bilirubin (total), collected unit (BILIT, BILIT_U)  | Listing only (units converted to µmol/L)  |
| Bilirubin (total), μmol/L (derived from BILIT
above)   | n, mean, sd, median, min, max, by visit   |
| Bilirubin (total), Out of range and Clinically significantly abnormal (BILIT_OR, BILIT_CS)              | # patients and % /category
(1 category BILIT_OR; Yes, 2 categories
BILIT_CS; Yes/No), by visit  |

Study SynAct-CS002 – Statistical Analysis Plan

| Bilirubin (conjugated), collected unit (BILIC,
BILIC_U)  | Listing only (units converted to $\mu$ mol/L)  |
|---|--|

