## 7.9.3 Thyroid Function

| Variable (CRF annotation)   | How to be presented   |
|---|---|
| TSH, collected unit  (TSH, TSH_U)                                 | Listing only (units converted to 10E3/L)  |
| TSH, 10E3/L (derived from TSH above)  | n, mean, sd, median, min, max, by visit   |
| TSH, Out of range and Clinically significantly abnormal (TSH_OR, TSH_CS)      | # patients and % /category
(1 category TSH_OR; Yes, 2 categories TSH_CS;
Yes/No), by visit      |
| Total T3, collected unit (TT3, TT3_U)   | Listing only (units converted to nmol/L)  |
| Total T3, nmol/L (derived from TT3 above)                                     | n, mean, sd, median, min, max, by visit   |
| Total T3, Out of range and Clinically significantly abnormal (TT3_OR, TT3_CS) | <pre># patients and % /category (1 category TT3_OR; Yes, 2 categories TT3_CS; Yes/No), by visit</pre> |
| Free T3, collected unit (FT3, FT3_U)  | Listing only (units converted to pmol/L)  |
| Free T3, pmol/L (derived from FT3 above)                                      | n, mean, sd, median, min, max, by visit   |

Study SynAct-CS002 – Statistical Analysis Plan

| Free T3, Out of range and Clinically significantly abnormal (FT3_OR, FT3_CS)  | <pre># patients and % /category (1 category FT3_OR; Yes, 2 categories FT3_CS; Yes/No), by visit</pre> |
|---|---|
| Total T4, collected unit (TT4, TT4_U)   | Listing only (units converted to nmol/L)  |
| Total T4, nmol/L (derived from TT4 above)                                     | n, mean, sd, median, min, max, by visit   |
| Total T4, Out of range and Clinically significantly abnormal (TT4_OR, TT4_CS) | <pre># patients and % /category (1 category TT4_OR; Yes, 2 categories TT4_CS; Yes/No), by visit</pre> |
| Free T4, collected unit (FT4, FT4_U)  | Listing only (units converted to pmol/L)  |
| Free T4, pmol/L (derived from FT4 above)                                      | n, mean, sd, median, min, max, by visit   |
| Free T4, Out of range and Clinically significantly abnormal (FT4_OR, FT4_CS)  | # patients and % /category
(1 category FT4_OR; Yes, 2 categories FT4_CS;
Yes/No), by visit      |

 Different laboratories might use different units. All values collected in different units than the units to be used for analysis will be converted, see section 3.6.

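### The SAP body's laboratory summaries have no multiple of the local ULN, no high/low split and no shift from baseline, so severity and direction of individual abnormalities cannot be counted by arm

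*SAP*

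**What the plan says.** Protocol 13.1 defines the primary safety endpoint as "The safety of AP1189 against placebo by evaluating adverse events (AEs), serious adverse events (SAEs), and laboratory abnormalities". SAP 2.1.2 names the same three components and adds: "See section 3.6 for details of the calculation of primary safety variables".

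The safety part of SAP 3.6 covers unit conversions, the QTcF formula, values below quantification and urine-culture categories. On reference ranges it says only: "All the clinical sites are using their local laboratory to measure safety parameters, which means that different reference intervals will apply". It does not define a laboratory abnormality.

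SAP 7.9.2 and 7.9.3 give each analyte the same treatment: n, mean, SD, median, minimum and maximum of the converted value by visit, plus two flags. For ALT the flags are "1 category ALT_OR; Yes, 2 categories ALT_CS; Yes/No), by visit"; for TSH, "1 category TSH_OR; Yes, 2 categories TSH_CS" with the same yes/no. Out of range has a single category, so high and low are merged.

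Protocol 19.1.1.1 works in multiples of the upper limit. Its rows include "ALT and/or AST increases > 3 to ≤ 5 x ULN" and "ALT and/or AST > 5 x ULN", a lower row starting at 1 times ULN, and a separate row for bilirubin above normal. Protocol 15.10 singles out liver and thyroid parameters in the safety evaluation that guides the choice of Part 2 design.

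**The concern.** The protocol describes liver abnormality by its size relative to each laboratory's own limit. The SAP reports either an absolute value pooled over laboratories with different limits, or a flag that gives neither size nor direction. The section that should define the primary safety variables does not supply the missing step.

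Three comparisons between arms are affected: how many subjects exceeded 3 or 5 times ULN, whether abnormal thyroid values were high or low, and whether an abnormality arose on treatment or was already present. The last matters because every subject is starting methotrexate, and Protocol 11.3.2 asks that liver increases be judged against pretreatment liver function and co-medication.

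**Working it through.** The plan states no figure on this point, so there is none to reproduce. The check traces the variables and then uses small illustrations. Assumed values are marked.

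**1. Trace through the SAP body.**
- SAP 3.1: six descriptive statistics for continuous variables; counts and percentages for categories.
- SAP 3.6: change from baseline is derived for CDAI, DAS28, HAQ-DI, FACIT-Fatigue, joint counts and cytokines. No liver or thyroid variable is listed.
- SAP 7: listings are planned for all safety variables. Flagging against protocol thresholds is stated for vital signs only.
- SAP 7.9.2 and 7.9.3: no value/ULN, no high/low category, no worst post-dose value and no shift table.

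**2. A pooled U/L value does not identify a band.** Assume local ALT upper limits of 35 to 60 U/L. The 3x boundary then runs from 3 × 35 = 105 to 3 × 60 = 180 U/L, and the 5x boundary from 5 × 35 = 175 to 5 × 60 = 300 U/L. One ALT value of 130 U/L gives:

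| Assumed ULN (U/L) | 130/ULN |
|---|---|
| 35 | 3.71 |
| 40 | 3.25 |
| 45 | 2.89 |
| 50 | 2.60 |
| 60 | 2.17 |

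The same number falls on both sides of the 3x line, and the planned table records every case as out of range.

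**3. What the descriptive statistics show.** Take 30 per arm, the minimum in Protocol 23.2.1.
- One subject rising from 1.0 to 3.6 × ULN moves the arm mean by (3.6 − 1.0)/30 = 0.087 × ULN.
- An arm with every ALT at 31 U/L has mean 31.0. So has an arm with 28 subjects at 22.5 and two at 150: (28 × 22.5 + 2 × 150)/30 = 930/30 = 31.0. With an assumed ULN of 40, those two are at 150/40 = 3.75 × ULN.
- Median, SD and maximum would separate these two arms. The maximum of 150 U/L still does not say how many subjects passed 3x, or whether 150 passes it at that laboratory.

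**4. Thyroid direction** (illustrative TSH values, with 6.0 and 3.8 taken as above and 0.2 as below the local range).
- Three at 6.0 and 27 at 2.0: mean (18 + 54)/30 = 2.40. Three at 0.2 and 27 at 2.0: mean (0.6 + 54)/30 = 1.82. The flag reads 3/30 in both arms; the mean shows the group direction.
- Three at 3.8, three at 0.2 and 24 at 2.0: mean (11.4 + 0.6 + 48)/30 = 2.00. Opposite individual shifts cancel. The flag reads 6/30, and SD, minimum and maximum hint at the spread, but no row gives the count in each direction.

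**5. New versus pre-existing.** If 3 of 30 are flagged at baseline and 3 of 30 at week 4, the number newly abnormal at week 4 can be anything from 0 (the same three) to 3 (three others). Counts by visit cannot distinguish these.

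**6. The protocol's own Phase 1 data.** Protocol 10.1.2 gives nine active and three placebo subjects per cohort. At 200 mg, Protocol 10.1.6 reports raised aminotransferases in three active and two placebo subjects: 3/9 = 33% against 2/3 = 67%. An out-of-range count alone therefore looks worse on placebo. The same section says the rises were most pronounced on active, up to 3.6x and 2.9x relative to the upper normal value; Protocol 11.3.2 gives the peak as 3x. On either figure, the contrast lay in severity.

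**The case against.** The strongest case against is that the SAP plans more than the flag, and that nothing in it breaks a protocol promise.

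- Median, SD, minimum and maximum accompany the mean, so an extreme ALT would appear in the by-visit maximum.
- Individual listings cover all safety variables. Abnormal laboratory findings can be adverse events, and SAP 7.10 tabulates events by severity and by action taken, including dose interruption and drug withdrawal.
- Protocol 19.1.1.1 is a management table for liver-enzyme elevation, not an endpoint definition. Its multiples apply to ALT and AST only.
- Protocol 21.1.9 uses local reference ranges to identify notable values, and the out-of-range flag is consistent with that. Apart from low values, it roughly captures the 1x ULN boundary and raised bilirubin.
- All analyses are descriptive, and no protocol section promises shift tables.
- The table shells are in Appendix 4, which is not among the supplied documents.

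Most of this stands and limits the point. A reader might infer that only means are reported, or that the plan cannot show whether thyroid values rose or fell. The documents do not support either: six statistics are planned, and means and medians by visit and arm show group direction. Nor do the Phase 1 figures establish a liver effect here. They come from very few subjects at a dose this trial does not use, and two of three placebo subjects also had raised values.

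The objection does not supply the missing counts. Listings and adverse-event tables support case review, but they give no between-arm number of subjects above 3x or 5x ULN, and the SAP names no ULN variable that would let a reader reconstruct one.

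**Conclusion.** The point holds as an inexpensive improvement to reporting. On the SAP body as written, the between-arm laboratory summaries cannot count subjects above 3x or 5x ULN, show the direction of individual thyroid abnormalities, or separate new from pre-existing elevations. SAP 2.1.2 also refers to section 3.6 for a calculation of laboratory abnormalities that is not there.

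No sample size or efficacy result changes. What is lost is resolution on one component of the primary safety endpoint, in the two organ systems that the protocol singles out. The statement about missing tables rests on the SAP text alone. The ULN and TSH values above are assumptions for illustration. If Appendix 4 already contains these tables, the remaining task is to describe them in the SAP body.

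**What to change.** For reporting only, with no change to any clinical rule:

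1. In SAP 3.6, define a laboratory abnormality against the local reference range. Derive value/ULN for ALT, AST and bilirubin, and low/normal/high for every analyte with a range.
2. In SAP 7.9.2, tabulate by arm each subject's worst ALT/AST after first dose as >1 to 3, >3 to 5 and >5 × ULN, with bilirubin shown separately as above normal or not.
3. In SAP 7.9.1 to 7.9.3, split each out-of-range count into low and high.
4. Add baseline-by-worst-value shift tables for liver and thyroid parameters. For thyroid, use low/normal/high, so that sites measuring free or total T3 and T4 are each classified against their own range.

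SAP 3.7 states that the interim analysis has already been done, so this applies to the final analysis. The cost is a lookup file of the local reference limits that sites already use, plus a few extra tables. No additional data are collected from subjects.
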